NON-INTERVENTIONAL (NI) STUDY PROTOCOL

Study information

Title	A Real-World Study Evaluating the Safety of Pantoprazole Sodium intravenous (IV) in Infants Aged 1 Month to <1 Year and Patients Aged 1 to <2 Years Using an Electronic Health Records Database from the United States
Protocol number	B1791096
Protocol version identifier	2.0
Date	10 February 2022
EU Post Authorization Study (PAS) register number	EUPAS45389
Active substance	Pantoprazole sodium (A02BC02)
Medicinal product	Protonix
Research question and objectives	Research Question: What are the incidence rates of potential safety events of interest in infants aged 1 month to <1 year and in patients aged 1 to <2 years who were treated with intravenous (IV) pantoprazole in the real-world setting? Primary Objective: To estimate the incidence of prespecified outcomes of interest in two separate cohorts, ie, infants aged 1 month to <1 year and patients aged 1 to <2 years with a diagnosis of gastroesophageal reflux disease (GERD)

	with or without erosive esophagitis (EE) and treated with IV pantoprazole.
	Secondary Objective 1: To estimate the incidence of prespecified outcomes of interest in infants aged 1 month to <1 year and patients aged 1 to <2 years treated with IV pantoprazole without a diagnosis of GERD or EE
	Secondary Objective 2: To provide the frequency of the 25 most common diagnostic codes occurring within 30 days prior to starting or on the date of start of IV pantoprazole (ie, index date) through 90 days of the last treatment with IV pantoprazole among infants aged 1 month to <1 year and patients aged 1 to <2 years with a diagnosis of GERD (regardless of EE diagnosis).
Author	[name]
	Epidemiologist, Safety Surveillance Research
	Pfizer, Inc.
	[name]
	[name]

This document contains confidential information belonging to Pfizer. Except as otherwise agreed to in writing, by accepting or reviewing this document, you agree to hold this information in confidence and not copy or disclose it to others (except where required by applicable law) or use it for unauthorized purposes. In the event of any actual or suspected breach of this obligation, Pfizer must be promptly notified.

Version	2.0.	10 February	72022
version	2.0.	TO redruary	/ 20122

ı.	TAB	BLE OF CONTENTS	
1.	TABLE (OF CONTENTS	3
2.	LIST OF	ABBREVIATIONS	5
3.	RESPON	ISIBLE PARTIES	7
4.	ABSTRA	ACT	8
5.	AMEND	MENTS AND UPDATES	12
6.	MILEST	ONES	13
7.	RATION	IALE AND BACKGROUND	13

2. LIST OF ABBREVIATIONS

Abbreviation	Definition	
AEP	Aetion Evidence Platform	
AE	Adverse event	
CDC	Centers for Disease Control and Prevention	
CI	Confidence interval	
DRESS	Drug Rash with Eosinophilia and Systemic Symptoms	
EE	Erosive esophagitis	
EHR	Electronic health record	
FDA	Food and Drug Administration	
GERD	Gastroesophageal reflux disease	
GPP	Good Pharmacovigilance Practices	
HCPCS	Healthcare Common Procedure Coding System	
ICD-9-CM	International Classification of Diseases, Nineth Revision, Clinical Modification	
ICD-10-CM	International Classification of Diseases, Tenth Revision, Clinical Modification	

Version 2.0, 10 February 2022

ID	Identification	
IEC	Independent ethics committee	
IRB	Institutional review board	
ISPE	International Society for Pharmacoepidemiology	
IV	Intravenous	
NASH	Nonalcoholic steatohepatitis	
NDA	New drug application	
NDC	National drug code	
NEC	Not elsewhere classified	
PASS	Post authorization safety study	
PK	Pharmacokinetics	
PMR	Post-Marketing Requirement	
PREA	Pediatric Research Equity Act	
SAP	Statistical analysis plan	
US	United States	
USPI	United States Prescribing Information	

4. ABSTRACT

Title: A Real-World Study Evaluating the Safety of Pantoprazole Sodium IV in Infants Aged 1 Month to <1 Year and Patients Aged 1 to <2 Years Using an Electronic Health Records Database from the United States

Version: 2.0

Date: 10 February 2022

Author: [name], Pfizer, Inc., Peapack, New Jersey

Rationale and background:

Protonix® (pantoprazole sodium) IV for Injection is indicated for short-term treatment (7 to 10 days) of adult patients with GERD and a history of EE [PROTONIX® IV (pantoprazole sodium) for injection, for intravenous use United States Prescribing Information (USPI)]. It is also indicated for the treatment of pathological hypersecretory conditions including Zollinger-Ellison Syndrome in adults. Protonix IV is currently not indicated for use in pediatric patients. The Food and Drug Administration (FDA) issued a requirement for a deferred study under the Pediatric Research Equity Act (PREA) for the treatment of GERD in patients 0 to 16 years of age as a Post-Marketing Requirement (PMR) number 145-1 in December 2004 [06 December 2004 letter to New Drug application (NDA) 20-988/S-027]. Currently, there is an ongoing clinical trial B1791089 conducted in patients 1 to 16 years of age. However, infants aged 1 month to <1 year cannot be enrolled into the ongoing clinical trial. Also, there may be insufficient number of patients aged 1 to <2 years enrolled in the ongoing trial. For these reasons, patients in both these two age-groups are being pursued to be included in this non-interventional study. This non-interventional study is designated as a Post-Authorization Safety Study (PASS) and is proposed voluntarily by Pfizer to collect safety data in two separate cohorts of infants aged 1 month to <1 year and patients aged 1 to <2 years who were treated with IV pantoprazole, with a primary focus on patients with a diagnosis of GERD with or without EE using an electronic health records database from the United States. In addition to this study, pharmacokinetic (PK) modeling and simulation is being pursued in lieu of an interventional clinical trial as another strategy to address this PMR.

Research question and objectives

Research Question:

What are the incidence rates of potential safety events of interest in infants aged 1 month to <1 year and in patients aged 1 to <2 years who were treated with IV pantoprazole in the real-world setting?

Within each study cohort (ie, infants aged 1 month to <1 year and in patients aged 1 to <2 years), the primary study objective is:

Version 2.0, 10 February 2022

(1) to estimate the incidence of prespecified outcomes of interest as described below under variables in patients with a diagnosis of GERD with or without EE and treated with IV pantoprazole.

The two secondary objectives are as follows: (1) to estimate the incidence of prespecified outcomes of interest in patients treated with IV pantoprazole without a diagnosis of GERD or EE, and (2) to provide the frequency of the 25 most common diagnostic codes occurring within 30 days prior to or on the date of initiation of IV pantoprazole through 90 days of the last treatment with IV pantoprazole in patients with a diagnosis of GERD (regardless of EE diagnosis).

Study design

Retrospective cohort study using Optum's longitudinal electronic health records (EHR) repository from the United States (US).

Study population

Two separate cohorts, ie, infants aged 1 month to <1 year and patients aged 1 to <2 years who received at least one administration of IV pantoprazole during a study period of 01 January 2007 to 31 December 2020 and those enrolled in the database for at least 30 days prior to the date of first administration of IV pantoprazole will be identified from the Optum's longitudinal EHR repository. In both cohorts, patients with International Classification of Diseases, Ninth Revision, Clinical Modification (ICD-9-CM) or International Classification of Diseases Tenth Revision, Clinical Modification (ICD-10-CM) codes indicating a preterm birth will be excluded. Within each cohort, 3 subgroups will be identified: (1) patients with ICD-9-CM or ICD-10-CM codes for GERD with EE, (2) patients with ICD-9-CM or ICD-10-CM codes for GERD but without EE, and (3) patients without diagnosis codes for GERD or EE.

Variables Exposure to IV pantoprazole will be identified from inpatient procedure and drug codes including National Drug Codes (NDC) and Healthcare Common Procedure Coding System (HCPCS) codes. The date of first administration of IV pantoprazole will be defined as the index date. For each outcome, patients will be followed from the index date to whichever of the following occurs first: occurrence of the outcome of interest, 90 days following the last date of IV pantoprazole administration, initiation of a separate IV pantoprazole infusion within 90 days following the discontinuation of IV pantoprazole administration, death, end of enrollment in the database, or end of study period (ie, 31 December 2020). The following outcomes of interest will be defined based on the presence of at least one ICD-9-CM or ICD-10-CM diagnosis code identified in the inpatient or outpatient setting during the follow-up period:

- Agranulocytosis
- Thrombocytopenia
- Leukopenia

- Pancytopenia
- Hypersensitivity (including anaphylactic reactions and anaphylactic shock)
- Hyperlipidaemia
- Hypertriglyceridemia
- Hyponatraemia
- Hypomagnesaemia
- Hypocalcaemia
- Hypokalaemia
- Diarrhea
- Vomiting
- Abdominal distension
- Hepatobiliary injury
- Urticaria
- Angioedema
- Stevens-Johnson syndrome
- Lyell syndrome
- Erythema multiforme
- Drug Rash with Eosinophilia and Systemic Symptoms (DRESS)
- Tubulointerstitial nephritis
- Photosensitivity
- Peripheral edema and
- Injection site thrombophlebitis

The other key variables of interest to be collected include demographic characteristics, comorbidities, and duration and dose of IV pantoprazole.

Data sources

Optum's longitudinal EHR repository from the US will be used for this study. The Optum EHR with Integrated Claims dataset contains electronic health records data with prescriptions, diagnoses, and provider information as well as practice management data and claims information for deterministically-matched patients. This dataset contains a combination of structured data (e.g. diagnoses, procedures, prescriptions) and information from unstructured data (e.g. drug rationale, provider notes) from the electronic health record and corresponding claims information for those instances. The claims are verified, adjudicated, adjusted, and de-identified. The database currently encompasses the claims and EHR data of more than 95 million patients with approximately 1.9 million patients aged less than 2 years from 01 January 2007 through 31 December 2020.

Study size

All eligible patients meeting inclusion/exclusion criteria will be included in the study. Based on preliminary feasibility, it is anticipated that 7,489 infants aged 1 month to <1 year and

6,657 patients aged 1 to <2 years who have been treated with IV pantoprazole will be eligible for inclusion in the study.

Data analysis

All statistical analysis will be performed in the two cohorts of interest, ie, infants aged 1 month to <1 year and in patients aged 1 to <2 years, separately using the Aetion Evidence Platform version 4.2. Descriptive statistics will be presented for the key variables to characterize the overall cohort treated with IV pantoprazole and the 3 subgroups defined based on the presence or absence of GERD and EE during the baseline period or on the index date. Incidence rates of outcomes of interest will be estimated as the number of patients with a specific outcome of interest during the follow-up period divided by the total person-time at risk and reported as incidence rate per 1,000 person-years with associated 95% confidence intervals (CIs). The CIs will be estimated using the exact method for event counts less than 10, assuming a Poisson distribution. Incidence rates for all outcomes of interest will be calculated in the overall cohort and in each of the 3 subgroups. Within the overall cohort and in the 3 subgroups, incidence rates will be estimated by duration of IV pantoprazole treatment (4 days, 4 days). Two sensitivity analyses will be performed as follows: (1) analysis will be repeated in both cohorts without exclusion criteria of at least 30-day enrollment prior to the index date to test the sensitivity to enforced 30-day enrollment period, and (2) analysis will be repeated in both cohorts, stratified by those patients identified via ICD-9-CM codes versus ICD-10-CM codes, respectively to test the sensitivity to ICD-9-CM versus ICD-10-CM coding for subgroup classification.

Milestones

Study protocol is planned to be submitted to the FDA by 20 August 2021 and study report is planned to be submitted to the FDA by 30 June 2022.

5. AMENDMENTS AND UPDATES

Amendment number	Date	Protocol section(s) changed	Summary of amendment(s)	Reason
1	10 February 2022	4, 8, 9.4.2	-Three outcomes of interest, i.e., hepatocellular injury/failure, jaundice, and hepatitis were consolidated into one category - hepatobiliary injury. -The ICD-9-CM and ICD-10-CM code lists used in the operationalization of some outcomes of interest were updated.	-There is a substantial overlap of hepatic conditions in the three outcomes of interest i.e., hepatocellular injury/failure, jaundice, and hepatitis; hence the outcome is simplified by combining the 3 separate categories into a single category of hepatobiliary injury. -Some inconsistencies in the use of ICD codes were noted; therefore, the code lists were updated.
1	10 February 2022	4, 9.4.2	- The outcomes of interest will be defined based on the presence of at least one ICD-9-CM or ICD-10-CM diagnosis code identified in the inpatient or outpatient setting during the follow-up period instead of only inpatient setting.	The outcomes of interest may occur in both inpatient and outpatient setting; hence it was added.
1	10 February 2022	4, 9.3.1, Table 2, 9.8, 9.10	The term 'dispensing' is replaced by 'administration'	Protonix IV administration is a correct term.
1	10 February 2022	9.8	An inconsistency in subgroups with respect to the primary objective and secondary objective 1 was corrected.	Primary objective includes analysis in 2 subgroups, i.e., patients with GERD and EE and patients with GERD, but without EE. The Secondary objective 1 includes analysis in the 3 rd subgroup of patients without a diagnosis of GERD or EE.

6. MILESTONES

Milestone	Planned date
Registration in the European Union (EU) PAS register	03 February 2022
Start of data collection	4 February 2022
End of data collection	31 March 2022
Final study report	30 June 2022

7. RATIONALE AND BACKGROUND

Protonix® (pantoprazole sodium) IV for Injection is indicated for short-term treatment (7 to 10 days) of adult patients with GERD and a history of EE [PROTONIX® IV (pantoprazole sodium) for injection, for intravenous use USPI]. It is also indicated for the treatment of pathological hypersecretory conditions including Zollinger-Ellison Syndrome in adults. Protonix IV is currently not indicated for use in pediatric patients.

The FDA issued a requirement for a deferred study under the PREA for the treatment of GERD in patients 0 to 16 years of age as a PMR number 145-1 in December 2004 (06 December 2004 letter to NDA 20-988/S-027). Currently, there is an ongoing clinical trial B1791089 conducted in patients 1 to 16 years of age. However, infants aged 1 month to <1 year cannot be enrolled into the ongoing clinical trial. Also, there may be insufficient number of patients aged 1 to <2 years enrolled in the ongoing trial. For these reasons, patients in both these two age-groups are being pursued to be included in this non-interventional study. This non-interventional study is designated as a PASS and is proposed voluntarily by Pfizer to collect safety data in two separate cohorts of infants aged 1 month to <1 year and patients aged 1 to <2 years who were treated with IV pantoprazole, with a primary focus on patients with a diagnosis of GERD with or without EE using an electronic health records database from the United States. In addition to this study, PK modeling and simulation is being pursued in lieu of an interventional clinical study as another strategy to address this postmarketing requirement.

B1791096 NON-INTERVENTIONAL STUDY PROTOCOL

Version 2.0, 10 February 2022

8. RESEARCH QUESTION AND OBJECTIVES

Research Question: What are the incidence rates of potential safety events of interest in infants aged 1 month to <1 year and in patients aged 1 to <2 years who were treated with IV pantoprazole in the real-world setting?

Primary Objective: To estimate the incidence of the following outcomes of interest in infants aged 1 month to <1 year and patients aged 1 to <2 years with a diagnosis of GERD with or without EE and treated with IV pantoprazole:

- Agranulocytosis
- Thrombocytopenia
- Leukopenia
- Pancytopenia
- Hypersensitivity (including anaphylactic reactions and anaphylactic shock)
- Hyperlipidaemia
- Hypertriglyceridemia
- Hyponatraemia
- Hypomagnesaemia
- Hypocalcaemia
- Hypokalaemia
- Diarrhea
- Vomiting
- Abdominal distension
- Hepatobiliary injury
- Urticaria
- Angioedema
- Stevens-Johnson syndrome
- Lyell syndrome
- Erythema multiforme
- DRESS
- Tubulointerstitial nephritis
- Photosensitivity
- Peripheral edema
- Injection site thrombophlebitis

Secondary Objective 1: To estimate the incidence of the above-mentioned outcomes of interest in infants aged 1 month to <1 year and patients aged 1 to <2 years treated with IV pantoprazole without a diagnosis of GERD or EE.

Secondary Objective 2: To provide the frequency of the 25 most common diagnostic codes occurring within 30 days prior to starting or on the date of start of IV pantoprazole (ie, index date) through 90 days of the last treatment with IV pantoprazole among infants aged 1 month

090177e1996138d1\Approved\Approved On: 23-Feb-2022 16:44 (GMT)

to <1 year and patients aged 1 to <2 years with a diagnosis of GERD (regardless of EE diagnosis).

9. RESEARCH METHODS

9.1. Study design

This will be a retrospective cohort study with no comparator group. No a priori hypotheses are specified. Descriptive analyses including an estimation of incidence rates will be performed.

9.2. **Setting**

The study will be conducted using Optum's longitudinal integrated EHR from the US¹, which is described in Section 9.5 This data source includes data from adjudicated administrative insurance claims, inpatient electronic health records, as well as outpatient EHR enabling capture of exposure to IV pantoprazole in the study population of interest. The study period will be defined from 01 January 2007 to 31 December 2020.

9.3. **Study population**

Two separate cohorts, ie, infants aged 1 month to <1 year and patients aged 1 to <2 years will be identified during the study period using the following inclusion and exclusion criteria.

9.3.1. **Inclusion criteria**

Patients must meet all of the following inclusion criteria to be eligible for inclusion in the study:

- 1. At least one administration of IV pantoprazole during the study period from January 1, 2007 to December 31, 2020, and
- 2. For the cohort of infants aged 1 month to <1 year (Cohort 1): Age 1 month to <1 year on the index date (ie, the date of first administration of IV pantoprazole); For the cohort of patients aged 1 to <2 years (Cohort 2): Age 1 to <2 years on the index date.
- 3. Patients must be enrolled in the database for at least 30 days prior to the index date

In addition to this 30-day lookback window, patients will be further excluded based on the occurrence of a history of outcomes of interest identified in Table 3 occurring prior to the index date.

9.3.2. **Exclusion criteria**

Patients meeting any of the following criteria will not be included in the study:

1. Patients with any of the following ICD-9-CM or ICD-10-CM codes occurring prior to or on the index date indicating a preterm birth or birth weight less than 2.36 kilograms will be excluded:

ICD-9-CM codes: 765.01-765.08; 765.10-765.19; 765.21-765.28

ICD-10-CM codes: P07.21-P07.26; P030-P039; P07.01-P07.03; P07.14-P07.18

The cut-off of birth weight less than 2.36 kilograms is defined based on a birth weight that is less than third percentile weight for males at birth obtained from Centers for Disease Control and Prevention (CDC) infant weight-for-age charts (available at URL: https://www.cdc.gov/growthcharts/html charts/wtageinf.htm). It is reasonable to assume that infants with birth weight less than 2.36 kilograms are most likely born preterm.

9.3.3. **Subgroups**

Within each cohort (ie, Cohort 1 and 2), 3 subgroups will be identified as follows:

- (1) Patients who have a diagnosis of GERD with EE: defined based on the presence of at least one of the ICD-9-CM or ICD-10-CM codes as shown in Table 1 and the presence of an additional ICD-9-CM or ICD-10-CM code for ulcer of the esophagus during the baseline period or on the index date, as shown in Table 1.
- (2) Patients who have a diagnosis of GERD without EE: defined based on the presence of at least one of the ICD-9-CM or ICD-10-CM codes and no ICD-9-CM or ICD-10-CM code for ulcer of esophagus during the baseline period or on the index date, as shown in Table 1.
- (3) Patients without a diagnosis of GERD or EE: defined as patients who do not have any of the ICD-9-CM or ICD-10-CM codes as shown in Table 1 during the baseline period or on the index date.

ICD-9-CM codes will be used to identify the subgroups prior to October 2015, after which ICD-10-CM codes will be used. No validated algorithm for GERD with or without EE were found to be available via literature review, therefore, a combination of clinical input, and the available codes identified in the literature will be used.² Additionally, there is no explicit ICD-9-CM code for GERD with/without esophagitis. Therefore, based on a cross-sectional study that examined the validity of diagnosis codes of benign upper gastrointestinal disorders using electronic patient records², and an online conversion tool maintained by the Center for Medicare Services and the Centers for Disease Control and Prevention (available at URL: https://icd.codes/convert/icd10-to-icd9-cm), the subgroups of GERD with or without EE will be determined using the operational definitions shown in Table 1:

Table 1. Operationalization of subgroups

Subgroup	ICD-10- CM Code	Description of ICD- 10-CM code	ICD-9- CM Code	Description of ICD-9- CM code
GERD without EE*	K21.0	GERD with esophagitis	530.10, 530.11, 530.12, 530.19	Esophagitis unspecified Reflux esophagitis, Acute esophagitis, Other esophagitis
	K21.9	GERD without esophagitis	530.81	Esophageal reflux
GERD with EE	K21.0, K21.9	GERD with or without esophagitis	530.10, 530.11, 530.12, 530.19, 530.81	Esophagitis unspecified Reflux esophagitis, Acute esophagitis, Other esophagitis Esophageal reflux
	AND			
	K22.1	Ulcer of esophagus	530.2	Ulcer of esophagus

^{*} Patients with any of the listed ICD-9-CM or ICD-10-CM codes and no ICD-9-CM code of 530.2 or ICD-10-CM code of K22.1 during the baseline period or on the index date will be included in the GERD without EE subgroup.

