9.6. Study size

There are no a priori hypotheses specified, and therefore, sample size calculations are not applicable. All eligible patients meeting inclusion/exclusion criteria will be included in the study. Based on preliminary feasibility, it is anticipated that 7,489 infants aged 1 month to <1 year and 6,657 patients aged 1 to <2 years who have been treated with IV pantoprazole will be eligible for inclusion in the study. Table 5 below shows the 95% confidence intervals around varying hypothetical frequencies of outcomes given a 7,489 and 6,657 patient sample, calculated using the Wilson score interval.

Table 5. Precision estimates for varying frequencies of outcomes for given 7,489 and 6,657 patient samples

Sample size	Outcome Frequency	N Events*	Lower 95% Bound	Upper 95% Bound
7489	0.002	15	0.0012	0.0033
	0.005	37	0.0036	0.0068
	0.01	75	0.0080	0.0125
	0.05	374	0.0452	0.0551
	0.1	749	0.0934	0.1070
	0.2	1498	0.1911	0.2092
6657	0.002	13	0.0011	0.0033
	0.005	33	0.0035	0.0070
	0.01	67	0.0079	0.0128
	0.05	333	0.0450	0.0555

10 February 2022

0.1	666	0.0931	0.1075
0.2	1331	0.1905	0.2097

^{*}Note: Event counts are rounded to nearest whole number

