For analyses of estimation of incidence rates of the outcomes of interest during follow-up, each analysis will be restricted to patients without a history of outcome of interest prior to the index date (ie baseline period); thus, for each analysis of a given specified outcome, a distinct sub-cohort will be used (i.e. for the estimation of the incidence of hepatitis, only patients with prevalent cases of hepatitis in the baseline period will be excluded from follow-up and will not contribute to person-time at risk).

For each outcome of interest, patients will be followed from the index date to whichever of the following occurs first (follow-up period):

- Occurrence of an outcome of interest,
- 90 days following the discontinuation of IV pantoprazole administration,
- Initiation of a separate IV pantoprazole infusion within 90 days following the discontinuation of IV pantoprazole administration, where a separate infusion is defined as the subsequent administration at least 7 days from the end of the previous infusion,
- Death,
- End of enrollment in the database,
- End of study period (ie, 31 December 2020).

Incidence rates of each prespecified outcome of interest will be estimated as the number of patients with a specific outcome of interest during the follow-up period divided by the total person-time at risk and reported as incidence per 1,000 person-years with associated 95% CIs, assuming a Poisson distribution. Exact Poisson confidence limits for the estimated rate are found as the Poisson means, for distributions with the observed number of events and probabilities relevant to the chosen confidence level, divided by time at risk.

$$egin{aligned} Y_l &= rac{\chi^2_{2Y,\;lpha/2}}{2} \ Y_u &= rac{\chi^2_{2(Y+1),\;1-lpha/2}}{2} \end{aligned}$$

- where Y is the observed number of events, Yl and Yu are lower and upper confidence limits for Y respectively, $\chi 2\nu$, a is the chi-square quantile for upper tail probability on ν degrees of freedom.

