More sensitive algorithms will be employed (i.e. algorithms based only on diagnostic codes, rather than more specific algorithms employing procedure and treatment codes in addition to diagnostic codes) for capturing outcomes to ensure safety events of interest are not missed.

However, the limitation of this approach is that, the incidence of some outcomes may be overestimated. Infants with a diagnosis of GERD with EE may be misclassified as those without EE. This is because a confirmed diagnosis of GERD with EE may not be available in infants due to reluctance of healthcare professionals to seek a confirmation via endoscopy. Also, those with a presumptive diagnosis of EE may be classified into the subset of infants with GERD alone. Prior to October 2015, ICD-9-CM codes were exclusively used to identify eligible patients, and GERD is not explicitly captured under this coding schema. ICD-10-CM codes provide additional granularity, but a validated code for erosive esophagitis and GERD is not available, nor well-established or validated in the literature. However, including patients identified using both coding schemes is important to increase sample size of this small population of pediatric patients with a rare condition and exposure. To examine the impact of different coding systems, a sensitivity analysis stratified by those patients identified via ICD-9-CM codes versus ICD-10-CM codes, respectively is planned. The counts of the top 25 most common conditions occurring within 30 days prior to or on the index date through 90 days of the last treatment with IV pantoprazole may include prevalent/comorbid conditions and not just conditions emerging following IV pantoprazole administration. This will however help generate hypotheses about unsuspected safety events in this patient population. Furthermore, a pre-planned sensitivity analysis stratifying by each code type will be performed for the analysis to understand if significant heterogeneity exists in this patient population with respect to the incidence of these outcomes following administration of IV pantoprazole. Finally, the study results may not be generalizable to infants aged 1 month to <1 year and patients aged 1 to <2 years outside of the commercially insured population.

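### Protocol 9.3.1 excludes patients from the study for a history of Table 3 outcomes, while 9.8 excludes them only from the analysis of the outcome concerned; the two rules define different cohorts and 9.3.1 should be brought into line

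*Protocol*

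**What the plan says.** Protocol 9.3.1 opens with "Patients must meet all of the following inclusion criteria to be eligible for inclusion in the study" and lists three numbered criteria: exposure, age and 30 days of enrollment. An unnumbered sentence follows. In addition to the 30-day window, it says, patients are "further excluded based on the occurrence of a history of outcomes of interest identified in Table 3 occurring prior to the index date". It refers to the Table 3 outcomes as a group and does not mention any particular analysis.

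Protocol 9.8 states the restriction differently: "each analysis will be restricted to patients without a history of outcome of interest prior to the index date (ie baseline period"), and "for each analysis of a given specified outcome, a distinct sub-cohort will be used". Its worked example is that for hepatitis "only patients with prevalent cases of hepatitis in the baseline period will be excluded from follow-up".

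Protocol 9.6 says that "All eligible patients meeting inclusion/exclusion criteria will be included in the study" and anticipates 7,489 infants in Cohort 1 and 6,657 patients in Cohort 2. It does not say whether a history exclusion had been applied when those counts were made.

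Neither the study population paragraph of the abstract nor the exclusion list in 9.3.2 contains an outcome-history exclusion.

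**The concern.** An exclusion placed under eligibility decides who is in the study at all. Under 9.3.1 as written, an infant with one vomiting code before the index date leaves every analysis, including those of hepatobiliary injury, the cytopenias and the skin reactions. Under 9.8 the same infant leaves only the vomiting analysis.

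The choice affects every denominator, the descriptive tables, the three GERD/EE subgroups and the code counts of secondary objective 2. It also decides whether the cohort sizes in 9.6, and the precision shown in Table 5, refer to the cohort that will be built.

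The wording matters in practice. Section 9.9 has the cohort-inclusion measures built from this protocol, requires that the protocol be followed strictly, and has all analyses implemented a second time by an independent team. Two careful teams could build different cohorts from these two sections.

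**Working it through.** **1. The two rules side by side**

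| | 9.3.1, read literally | 9.8 |
|---|---|---|
| Level | study entry | one analysis |
| Trigger | history of Table 3 outcomes, not tied to the one analysed | history of the outcome analysed |
| Patient with a prior vomiting code, hepatobiliary analysis | out | in |
| Sub-cohorts at the index date | all 25 identical | one for each outcome |
| Pre-index Table 3 codes in secondary objective 2 | none possible | retained |

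If 9.3.1 is applied first, nobody with a prior Table 3 code remains. The 9.8 restriction then has nothing left to remove, and its sub-cohorts cannot be distinct. Secondary objective 2 counts codes from 30 days before the index date, so the Table 3 codes in the pre-index part of that window would be absent by construction. Section 9.10 expects those counts to be mixed: they "may include prevalent/comorbid conditions and not just conditions emerging following IV pantoprazole administration". These consequences need no assumption about prevalence.

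**2. The plan's own figures (9.6, Table 5)**

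Inputs: N = 7,489 and 6,657, two-sided 95% Wilson score interval, event counts rounded to whole numbers.

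Limits = [p + z²/(2N) ± z·√(p(1−p)/N + z²/(4N²))] / (1 + z²/N), with z = 1.96.

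For N = 7,489 and 75 events, p = 75/7,489 = 0.01001:
- centre = (0.010015 + 0.000256)/1.000513 = 0.01027
- half-width = 0.00227
- limits 0.0080 to 0.0125, as printed.

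All 12 rows of Table 5 reproduce to four decimals. Its arithmetic is right; the open question is whether its N is the N of the cohort that will be built.

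**3. Illustrative loss under the literal 9.3.1 reading**

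Let q be the share of patients with at least one prior Table 3 outcome. The protocol gives neither q nor any single prior prevalence p. Assume, for illustration only, the same p for all 25 outcomes and independence between them:

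q = 1 − (1 − p)^25; patients left = N(1 − q).

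Under 9.8 each analysis keeps N(1 − p).

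| Assumed p | q | Left under 9.3.1 (Cohort 1 / 2) | Left per analysis under 9.8 (Cohort 1 / 2) |
|---|---|---|---|
| 0.5% | 12% | 6,607 / 5,873 | 7,452 / 6,624 |
| 1% | 22% | 5,825 / 5,178 | 7,414 / 6,590 |
| 2% | 40% | 4,519 / 4,017 | 7,339 / 6,524 |
| 3% | 53% | 3,497 / 3,109 | 7,264 / 6,457 |
| 5% | 72% | 2,077 / 1,847 | 7,115 / 6,324 |

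Positive correlation between outcomes lowers q. In the extreme, where the same patients carry every prior code, q falls to p and the two rules remove equally many patients.

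**4. Effect on precision**

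If q were 50%, Cohort 1 would fall to 3,744. At a frequency of 0.01 the Wilson limits would widen from 0.0080–0.0125 to 0.0073–0.0137.

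**The case against.** The strongest reply is that the protocol already contains the operative rule. Section 9.8 is detailed, speaks of distinct sub-cohorts and gives an example that only works per outcome. The 9.3.1 sentence is not one of the numbered criteria, does not say that any single Table 3 outcome suffices, and can be read as introducing the washout that 9.8 then specifies. The abstract and 9.3.2 list no such exclusion, and 9.10 expects prevalent conditions among the secondary objective 2 counts. Double implementation with adjudication (9.9) makes a silent error less likely.

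Most of this stands: the per-outcome rule is very probably what is meant. It does not remove the contradiction. Eligibility is where a programmer looks to build the cohort, and adjudication between two teams needs a text that settles the matter. The example in 9.8 also names hepatitis, which the current outcome list no longer carries as a separate outcome.

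Two stronger readings are tempting and fail.

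- A reader might infer that the sections use different look-backs: any time before index in 9.3.1, the baseline period in 9.8. But 9.8 also says prior to the index date, and equates that with the baseline period. No difference is shown.
- A reader might infer that 9.3.1 would strip out much of the cohort and leave a healthier remainder, because Table 3 includes vomiting and diarrhea. That is plausible, but no passage gives a prior prevalence. The 72% figure requires 5% for every outcome, including very specific ones such as DRESS, which has no ICD-9-CM code in Table 3. Independence is also assumed, although related outcomes such as the electrolyte disorders may well cluster.

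**Conclusion.** The contradiction is real and visible in the text: a study-level exclusion in 9.3.1 against an outcome-specific one in 9.8. Applied literally, 9.3.1 defines a cohort that the rest of the protocol does not intend and leaves the 9.8 rule without effect.

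The direction of the effect is certain, since the any-outcome rule can only remove at least as many patients as the per-outcome rule. Its size is unknown. The range of about 12% to 72% rests on equal prior prevalences of 0.5% to 5% and on independence, neither of which comes from the documents.

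Nor can it be said that the 7,489 and 6,657 are wrong. Section 9.6 does not state whether they precede or follow a history step, and Table 5 is correct for those N. The point is therefore a contradiction in the eligibility text, to be corrected before analysis, and not a proven large loss of patients.

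**What to change.** Delete the sentence from 9.3.1, or replace it with wording such as: *A patient with a record of a given Table 3 outcome before the index date is excluded only from the incidence analysis of that outcome (see 9.8), and remains in the cohort for all other analyses and tables.*

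Confirm in 9.6 that 7,489 and 6,657 were counted without an any-outcome history exclusion. If they were not, recount and regenerate Table 5. Check that both implementations of the cohort build follow the per-outcome rule.

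The cost is a one-sentence correction, one confirming statement and a check of the cohort build. No new data are needed.
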